5.4 Sensitivity Analyses

In case of a violation of the normality assumption of the residuals, the primary analysis will be repeated with log transformed dependent variable, where appropriate.

Results of the post-hoc group comparisons will then be presented as adjusted mean factors with corresponding 95%- Wald confidence intervals (resulting from back-transformation of the adjusted mean differences) and p-values will be given.

The primary endpoint and the secondary endpoint a) will additionally be analyzed using the complete case data only, without adjustment for baseline discontinuation symptoms, and in the per protocol population.

Further sensitivity analyses on imputed data might be performed, see Section 5.2 for details. All endpoints might be analysed in the per protocol population.

5.5 Safety Evaluation

All safety endpoints for the treatment groups will be analysed descriptively, i.e. event rates with two-sided 95% confidence intervals will be given.

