2.3 Sample Size

A medium effect size of $f=0.22$, a significance level of $\alpha=0.05$, and a power of 80% were assumed. This resulted in 168 patients needed in total (i.e. 42 per group) using an ANOVA model (with main effects and interactions). Furthermore, with an expected drop-out rate of at most 15%, in total 196 patients need to be recruited (i.e. 49 per group).

Sample size calculation was conducted using G*Power (version 3.1.9.2).

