2.4 Framework

Test for difference will be applied for all endpoints. The primary endpoint is tested in confirmatory manner. A significance level of 0.05 will be used. All secondary and safety endpoints will be analysed in an exploratory way and thus, no adjustment for multiplicity will be applied.

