3.1 Confidence Intervals and *P* Values

All applicable statistical tests will be two-sided and will be performed using a 5% significance level. All confidence intervals presented will be 95% and two-sided. Analyses of secondary and safety outcomes will be performed exploratory without adjustment for multiple testing.

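### SAP Sections 2.4 and 5.5 conflict on safety endpoints, and apart from recurrence and DESS no discontinuation-versus-continuation safety contrast is specified

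*SAP*

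**What the plan says.** Section 2.4 (Framework) states: "Test for difference will be applied for all endpoints". It continues: "All secondary and safety endpoints will be analysed in an exploratory way and thus, no adjustment for multiplicity will be applied". That sentence lowers the status of the safety analyses and drops the multiplicity adjustment. It does not take safety out of the testing rule.

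Section 3.1 repeats the point: "Analyses of secondary and safety outcomes will be performed exploratory without adjustment for multiple testing". It also says: "All applicable statistical tests will be two-sided and will be performed using a 5% significance level".

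Section 5.5 is a single sentence: "All safety endpoints for the treatment groups will be analysed descriptively, i.e. event rates with two-sided 95% confidence intervals will be given". It names no test, model or difference between groups.

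Section 1.3.3 lists four safety endpoints: (a) BDI-II and MADRS depressive symptoms, including suicidality and recurrence; (b) the current treatment-effect rating; (c) adverse events; (d) clinical impression. Section 3.3.4 puts every randomised patient in the safety set.

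**The concern.** An analyst cannot satisfy both sections. Section 2.4 calls for a comparison of safety endpoints, and Section 5.5 provides only single-group summaries.

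The trial randomises discontinuation against continuation, so each safety event has a randomised comparison that would estimate the excess directly. Section 5.5 does not use it. Anyone wanting the excess must compare separate intervals by eye, and overlap of separate intervals is a poor guide to whether a difference interval excludes zero. For adverse events and suicidality in a trial of stopping antidepressants, a real excess could be under-read.

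There is also a mismatch of type. BDI-II, MADRS and the treatment-effect rating are scores, and an event rate does not summarise a score unless a cut-off is defined. Section 5.5 defines none.

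**Working it through.** **1. Planned group size.** Section 2.3 takes f = 0.22, 5% significance and 80% power, and arrives at 168 evaluable patients, 42 in each of the four groups. For an interaction with 1 numerator degree of freedom and four groups, the noncentrality is f² × N. At f = 0.22 the smallest N with 80% power is 165 (power 0.802). Rounded up to four equal groups this is 168 (power 0.809), so the plan's 168 reproduces. The recruited total of 196 corresponds to 42 × 1.15 = 48.3, rounded up to 49 per group; dividing by 0.85 would give 198 in total, a small difference. With 1:1:1:1 allocation (Section 2.1) the safety set is planned as 49 per group, or 2 × 49 = 98 discontinuing versus 98 continuing.

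**2. Which harms already have a contrast.**

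| Outcome | Discontinuation-versus-continuation estimate? | Where |
|---|---|---|
| Discontinuation symptoms (DESS AUC, primary) | Yes, adjusted mean difference | 5.3.1 |
| DESS over follow-up | Yes, adjusted mean difference | 5.3.2 |
| Recurrence to week 13 | Yes, odds ratio | 5.3.2 |
| Recurrence to week 52 | Yes, hazard ratio | 5.3.2 |
| Adverse events | No | 5.5 |
| Suicidality | No | 5.5 |
| BDI-II and MADRS scores | No | 5.5 |
| Treatment-effect rating | No | 5.5 |
| Clinical impression | No | 5.5 |

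**3. What a contrast would add.** The SAP states no safety rates, so all counts here are assumptions. Single-group intervals are Clopper-Pearson. Difference intervals are Newcombe: with Wilson limits (l, u) for each proportion p,

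lower = d − √[(p1 − l1)² + (u2 − p2)²]; upper = d + √[(u1 − p1)² + (p2 − l2)²].

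*Assumed 14/98 versus 4/98.* p1 = 14.29%, Wilson 8.70 to 22.56; p2 = 4.08%, Wilson 1.60 to 10.03; d = 10.20 points.
- Lower: 10.20 − √(5.59² + 5.95²) = 10.20 − 8.16 = 2.0.
- Upper: 10.20 + √(8.27² + 2.48²) = 10.20 + 8.63 = 18.8.
- The separate Clopper-Pearson intervals are 8.0 to 22.8% and 1.1 to 10.1%. They overlap, although the difference interval excludes zero.

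*The same rates within one information level, 7/49 versus 2/49.* The separate intervals are 5.9 to 27.2% and 0.5 to 14.0%. The difference is 10.2 points (-1.8 to 22.9).

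*Assumed 5/98 versus 1/98.* p1 = 5.10%, Wilson 2.20 to 11.39; p2 = 1.02%, Wilson 0.18 to 5.56; d = 4.08 points.
- Lower: 4.08 − √(2.90² + 4.54²) = 4.08 − 5.39 = -1.3.
- Upper: 4.08 + √(6.29² + 0.84²) = 4.08 + 6.35 = 10.4.

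**Range over assumed counts at 98 versus 98:**

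| Discontinuing | Continuing | Difference (points) | 95% CI |
|---|---|---|---|
| 3 | 1 | 2.0 | -2.9 to 7.7 |
| 5 | 1 | 4.1 | -1.3 to 10.4 |
| 10 | 4 | 6.1 | -1.4 to 14.1 |
| 14 | 4 | 10.2 | 2.0 to 18.8 |
| 20 | 10 | 10.2 | 0.04 to 20.3 |

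**The case against.** Descriptive safety reporting is a common and legitimate choice, and the trial is not sized for any safety event. Section 2.4 can be read as a short statement that the trial tests difference rather than equivalence or non-inferiority. Section 3.1 restricts its rule to applicable tests, and Section 5.5, as the more specific section, would then govern. On that reading one exempting clause in Section 2.4 removes the conflict. A reader could also compute risk differences from published counts. Most of this stands: the descriptive choice is not an error in itself, and nothing in the SAP makes overlap of intervals a decision rule. But the exempting clause is not there, and Section 5.5 still has no summary suited to the scores.

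Three stronger readings are tempting, and the SAP does not support them.

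- A reader might infer that the trial never estimates the excess harm of discontinuing. It does so for DESS and for recurrence, which is itself named within safety endpoint (a).
- A reader might take it as settled that safety will be shown as four intervals of about 49 patients. Section 5.5 refers only to the treatment groups; the four randomised groups and two pooled arms are both possible. The point holds either way, since the pooled single-arm intervals in the 14/98 versus 4/98 example also overlap.
- A reader might infer that a contrast would reveal a clear signal. That depends on the counts. Within one information level the example interval includes zero, and for rare events even 98 versus 98 often does.

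**Conclusion.** The point holds as a narrow one. Sections 2.4 and 5.5 give incompatible instructions for safety. For adverse events, suicidality, the BDI-II and MADRS scores, the treatment-effect rating and clinical impression, the randomised comparison goes unused. The primary result is unaffected.

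The gain from a contrast rests on assumed counts. It is material for events of moderate frequency with a large excess, and small for rare events, where the interval would mainly show how much excess cannot be ruled out. This is a cheap improvement to reporting and does not invalidate the plan.

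**What to change.** In Section 5.5:

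- Keep the event rates with 95% intervals, and state that they are given for the four randomised groups.
- For each safety event, add the discontinuation-minus-continuation risk difference with a 95% interval: within the open groups, within the hidden groups, and averaged over both (planned 98 versus 98; for example Newcombe within levels and Mantel-Haenszel for the average).
- For BDI-II, MADRS and the treatment-effect rating, replace event rates with group summaries and mean differences with 95% intervals.
- Label all of these exploratory and unadjusted.

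In Section 2.4, replace the all-endpoints wording so that it describes what Section 5.5 does for safety.

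The cost is SAP wording and a few table columns, with no new data. The downside is more unadjusted exploratory intervals. The average can also hide a difference between open and hidden groups, which is why the within-level rows should be shown beside it.

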5.6 Additional Analyses

We assume that the relationship between treatment expectation and discontinuation symptom load will vary according to stress ratings, prior side effects of antidepressant medication, prior discontinuation experience, neuroticism, anxiety, somatosensory amplification, and illness framework. In case of a significant interaction within the primary analysis, individual moderators will be included as 3rd factor in the model and three-way interactions will be analysed.

Saliva and blood samples will be taken as objective markers of AM blood serum level and stress, and optional participation in rsfMRI measurements will be scheduled.

As an objective marker, salivary cortisol awakening response and salivary alpha-amylase activity will be assessed. Salivary analyses will be conducted in the laboratory of the Institute of Medical Psychology and Behavioral Immunobiology, University Hospital Essen, as part of central scientific project Z02 within our CRC 289 Treatment Expectation.

Concerning analysis of the blood samples, we check adherence to study medication intake by comparing AM blood serum levels at t1 and t9 using paired t-tests per respective continuation (no relevant difference expected) or discontinuation group (relevant difference expected). We will assess whether AM blood serum levels lie within therapeutic range at t1 and exploratively examine the relationship between initial AM blood serum levels and discontinuation symptom load reported by the two discontinuation groups with correlation analyses. We hypothesize a positive correlation between initial AM blood serum levels and discontinuation symptom load among discontinuation groups.

In order to identify interindividual differences in effects of expectation on health outcome, brain imaging data on functional and structural connectivity will be collected and contributed to central scientific project Z03 within CRC 289 Treatment Expectation. Functional and structural imaging data from (i) rsfMRI, (ii) 3D-MPRage T1-weighted sequence, and (iii) Diffusion Tensor Imaging (DTI) will be acquired using a 3T MR system (Trio, Siemens Healthcare, Erlangen, Germany at the Institute of Systems Neuroscience, director [name]) with a 64-channel head/neck coil. Standardized MR protocols are provided by Z03, who will later use this data for pooled and meta-analytic analyses.

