1.2 Study Objective

This study aims to disentangle pharmacological from expectation effects and their interaction during discontinuation of antidepressants and explore their underlying processes. More specifically the following questions and hypotheses were stated:

- How do treatment and treatment expectation contribute to discontinuation symptom load? Treatment (discontinuation of AM vs. continuation) and treatment expectation (high vs. medium) interact in modulating discontinuation symptom load among remitted major depressive disorder (MDD) patients over the course of the experimental phase.
- In what way can discontinuation symptom load be affected by treatment expectation, i.e. the placebo-effect, alone? Remitted MDD patients who remain on their antidepressant medication will show a higher discontinuation symptom load with moderate than with high expectation.
- In what way can the discontinuation symptom load be affected by pharmacological factors alone? Remitted MDD patients with moderate treatment expectation will show a higher discontinuation symptom load if antidepressant medication is discontinued versus if antidepressant medication is continued.
- In what way does the discontinuation symptom load differ between high and moderate treatment expectation? Remitted MDD patients who discontinue their antidepressant

medication will show a higher discontinuation symptom load with high than with moderate treatment expectation.

- The relationship between treatment expectation and discontinuation symptom load will vary according to stress ratings, prior side effects of antidepressant medication, prior discontinuation experience, neuroticism, anxiety, somatosensory amplification, and illness framework.

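### The moderator hypothesis is analysed only if the primary treatment-by-expectation interaction is significant, so a stated study question can be left with no prespecified analysis

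*SAP*

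**What the plan says.** SAP Section 1.2 gives five questions and hypotheses. The fifth begins "The relationship between treatment expectation and discontinuation symptom load will vary according to stress ratings" and goes on to name six further characteristics: prior side effects, prior discontinuation experience, neuroticism, anxiety, somatosensory amplification and the patient's view of the illness. It carries no condition. Section 4.5 defines the scoring of all seven, and Table 1 in Section 2.6 schedules them as possible modulators.

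Section 5.6 repeats the assumption and then sets the rule: "In case of a significant interaction within the primary analysis, individual moderators will be included as 3rd factor in the model", with three-way interactions to be examined. The SAP does not say what happens to the moderators otherwise.

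Section 5.3.1 makes the interaction of the two randomised factors the primary test. If its p-value is above 0.15, the interaction is dropped and the two main effects are assessed. Section 3.1 sets the level: "All applicable statistical tests will be two-sided and will be performed using a 5% significance level". Section 2.3 sizes the trial: "A medium effect size of $f=0.22$, a significance level of $\alpha=0.05$, and a power of 80% were assumed", and "This resulted in 168 patients needed in total (i.e. 42 per group) using an ANOVA model (with main effects and interactions").

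**The concern.** The hypothesis and the gate concern different quantities. The hypothesis asks whether the effect of expectation differs between patients, for instance between those with high and low stress. The gate asks whether the effect of expectation, averaged over all patients, differs between discontinuation and continuation. Neither implies the other. Expectation could matter more for anxious patients equally in both treatment arms, which gives no two-way interaction at all. Or the two-way interaction could run in opposite directions in two kinds of patient and average to nothing, which is strong moderation with a shut gate.

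The gate also fits poorly with Section 5.3.1. For p between 0.05 and 0.15 the interaction stays in the model but no moderator is examined. For p above 0.15 the plan moves to main effects, where expectation-by-moderator is the natural term, and again none is examined.

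At stake is one of five listed hypotheses. If the gate stays shut, any moderator result later reported is post hoc, although the variables were collected for this purpose.

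**Working it through.** **Inputs.** From Section 2.3: f = 0.22, alpha = 0.05, power 80%, 168 evaluable and 196 recruited patients. From Section 2.1: four equal groups in a 2x2 factorial. From Section 3.1: two-sided 5%. From Section 5.3.1: the gate is the treatment-by-expectation interaction, a test with 1 numerator df. From Section 3.3.1: the primary population is all randomised patients.

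**Formula.** Power is the probability that a noncentral F variable with df1 = 1, df2 = N − 4 and noncentrality λ = f² × N exceeds the 5% critical value of the central F. The gate stays shut with probability 1 − power.

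**The plan's own figure.**
- The smallest N that reaches 80% power is 165 (power 0.802; N = 164 gives 0.7997). Rounded up to four equal groups this is 168, as stated.
- At N = 168, λ = 0.22² × 168 = 8.13, the critical value is 3.90 and power is 0.809.
- With 2 or 3 numerator df the required N would be 203 or 230, so the plan sized a 1-df effect, consistent with the interaction test.
- For dropout, 168 / 0.85 = 197.6, which is 198 patients against the 196 stated. The difference is immaterial here.

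**Probability that the gate stays shut.** Removing 3 further df for the covariates in Section 5.3.1 changes these values only in the fourth decimal place.

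| True interaction f | N = 168 | N = 196, all with full data |
|---|---|---|
| 0.22 (plan's assumption) | 19.1% | 13.5% |
| 0.20 | 26.9% | 20.4% |
| 0.15 | 51.1% | 44.8% |
| 0.11 | 70.6% | 66.5% |
| 0.10 | 74.8% | 71.4% |
| 0 | 95% | 95% |

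Only the first row is the plan's own. The others are assumptions that show the range.

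If f = 0.22 is the effect before baseline adjustment, the t1 covariate raises the effective f to 0.22 / √(1 − r²). The SAP gives no r. For an assumed r of 0.3 to 0.7 the probability falls to between 15.6% and 2.2% at N = 168, and between 10.5% and 1.0% at N = 196.

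**Two illustrations of the mismatch.** Both assume a binary moderator split 50:50 and N = 168.
- The planned interaction (0.22) exists in one half of the patients and is absent in the other. The average is 0.22 / 2 = 0.11 and the gate is shut in about 71% of trials.
- The interaction has size 0.22 in each half with opposite sign. The average is 0 and the gate is shut in 95% of trials. The three-way term itself has f = 0.22 and about 81% power if it is tested.

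**Cost of removing the gate.** If all seven moderator effects are null and the tests are independent, the chance of at least one p < 0.05 is 1 − 0.95⁷ = 30.2%.

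**The case against.** The gate can be defended as a prespecified, conservative choice. The trial is sized for a 1-df two-way effect and claims no power for three-way terms, so holding back seven weakly powered tests until the two-way effect appears is transparent. It also limits false positives to some degree: if every effect is null, seven ungated tests give up to about 30% chance of a false positive, whereas with the gate that chance cannot exceed about 5%, because the gate must open first. The analyses stand under additional analyses and no primary or secondary inference depends on them. Section 1.2 can be read as the expectation and Section 5.6 as the rule for when it is examined, so this is not a plain contradiction.

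Much of this stands, and it keeps the point small. A reader might infer that the gate protects no error rate because these tests are already declared exploratory. The SAP does not support that. Sections 2.4 and 3.1 give exploratory, unadjusted status to secondary and safety outcomes only, the status of the moderator models is not stated, and the gate gives the limited protection just described.

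What the defence does not answer is the mismatch of quantities. Waiting for the average two-way interaction does not screen for an expectation-by-moderator effect, and it tends to close when moderation dilutes or cancels that average.

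**Conclusion.** The point holds as a cheap improvement. Followed as written, the SAP can leave a listed hypothesis with no prespecified analysis, because the condition in Section 5.6 is a test of something else.

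A reader might take the 80% power to mean that the hypothesis is skipped with at least 20% probability under the trial's own assumptions. That is not supported. The stated power is the planned minimum, so about 20% is a ceiling: 19% at N = 168 and about 13.5% if all 196 patients carry full information, possibly less after baseline adjustment. Values above 20% need a true interaction below the assumed one, roughly below 0.22 at N = 168 or 0.20 at N = 196. The 71% at f = 0.11 is such a case and rests on an assumption that the SAP does not make.

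The argument therefore rests mainly on the mismatch and only secondarily on the percentages. The primary analysis and its error rate are untouched.

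**What to change.** In Section 5.6, remove the condition on a significant interaction. State that the seven moderator models will be fitted whatever the primary interaction p-value, that they are exploratory, and that estimates with 95% confidence intervals will be reported. Tie the model to Section 5.3.1: test the three-way term if the treatment-by-expectation interaction is retained, otherwise expectation-by-moderator in the main-effects model.

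This needs no new data or patients. The cost is up to seven more unadjusted tests in trials where the gate would have been shut, with the false-positive chance of about 30% shown above if all are null and independent. The SAP should therefore also say that the results are hypothesis-generating only.

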2.2 Randomization and Blinding

Stratified block randomization was used with variable block sizes.

Stratification variables were

- intake duration with 24 months as a marker for long-term intake (<24 months of AM vs. \geq 24 months, 3:7)
- risk of developing discontinuation symptoms associated with the antidepressant medication (moderate vs. higher or unknown risk, 1:1).

The script for the generation of a randomisation list was written by the responsible statistician of the IMBE and transferred to a study-independent employee of the IMBE who created the final randomization list using a new random seed.

The statistic software R (version 4.1.2) (R, 2021) and the package *blockrand* (Snow 2020) was used.

Randomization lists were handed to study staff who have no personal contact to study participants.

The staff responsible for analyses will be blinded with regard to group allocation. The study physician, the study psychologist, as well as supporting student assistants and the study participants are - in the case of assignment to one of the two hidden groups - blinded. Correspondingly, they are unblinded in case of assignment to one of the two open groups. The persons responsible for randomization are unblinded, but have no contact with the study participants. The study physician and the study psychologist are informed that the study participants have been assigned either to the (OD) open-discontinuation group, (OC) open-continuation group, or to one of the two hidden conditions, i.e. either (HD) hidden-discontinuation, or (HC) hidden-continuation. In this case, the study physician and the study psychologist have no knowledge of whether the study participant is in group (HD) or (HC). The information whether the participants belong to the groups (OD) or (OC), or to one of the two hidden groups (HD) or (HC), will be communicated by the study physician or the study psychologist.

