4.2 Eligibility

The number of ineligible patients randomised, if any, will be reported, with reasons for ineligibility. Ineligible patients are those who do not fulfil inclusion criteria or who show exclusion criteria:

Inclusion criteria

1. Adult patients (18-75 years) with fully remitted MDD, single or recurrent, as main diagnosis confirmed by prescribing physician and SCID-5-CV (Beesdo-Baum et al., 2018; First et al., 2016)
2. Intake of SSRI/SNRI (citalopram: 20-40mg, escitalopram: 10-20mg, sertraline: 75-150mg, venlafaxine: 75-150mg, duloxetine: 60-100mg, paroxetine: 20-40mg) or NaSSA (mirtazapine: 30-45mg)
3. Discontinuation wish by patient, supported by prescribing physician
4. Fulfilment of the German S3 national guideline recommendations for treatment of Major Depressive Disorders to discontinue AM: a) response to AM, b) symptom remission for at least four months (first episode)/ 2 years (2 or more episodes with significant functional impairment) and c) concurrent intake of antidepressant medication (at least 4 weeks on a steady dose)

Exclusion criteria

1. Acute or chronic somatic illness and/or intake of medication which might interfere with depressive disorder, AM or proposed study
2. Acute suicidality, psychotic symptoms, substance abuse or addiction within the last 12 months, current mania, or hypomania confirmed by SCID-5-CV or other psychopathology which might interfere with depressive disorder, AM or proposed study
3. Any history of bipolar disorder or psychosis confirmed by SCID-5-CV
4. Severe stressful life events (e.g., death of a family member) within six months prior to study participation
5. Insufficient German language proficiency.
6. No informed consent.

7. MRI-specific exclusion criteria, if applicable: phobic anxiety, claustrophobia, ferromagnetic implants, etc.

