5.3.1 Analysis of Primary Endpoint

A linear model (ANCOVA) will be used with the following variables:

- Dependent variable:
 - AUC value based on DESS scores t2-t9 (see Section 5.1.1)
- Independent variables:
 - Random group as two factors (i.e. 1st factor: treatment discontinuation vs continuation; 2nd factor; high vs. medium expectation) and their interaction
 - The following stratification variables of the randomization process:
 - *intake duration with 24 months as a marker for long-term intake (<24 months of AM vs. >24 months)*
 - *risk of developing discontinuation symptoms associated with the antidepressant medication (moderate vs. higher or unknown risk)*
 - The corresponding pseudo baseline value (t1) will additionally be included as covariate.

Primary interest lies in the interaction between the two factors describing the random group. The post-hoc comparisons between the subgroups will be addressed exploratively. If the corresponding p-value (for the interaction) is >0.15 the model will be calculated without the interaction and the independent main effects of the 2 factors will be assessed.

Normal distribution of the residuals will be checked graphically via a histogram of residuals. If the assumption of normally distributed residuals is clearly violated, a sensitivity analysis using the log-transformation for the dependent variable will be performed to judge the robustness of the results.

Adjusted mean values and adjusted effect estimators (mean differences) with corresponding 95% Wald confidence intervals and p-values will be given.

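### The exploratory correlation of initial serum level with symptom load pools seven drugs without a stated drug adjustment, so between-drug and within-drug differences are mixed

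*SAP*

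**What the plan says.** Section 5.6 of the SAP will "exploratively examine the relationship between initial AM blood serum levels and discontinuation symptom load reported by the two discontinuation groups with correlation analyses". The next sentence gives the expected direction: "We hypothesize a positive correlation between initial AM blood serum levels and discontinuation symptom load among discontinuation groups". Nothing is said about drug, risk stratum, transformation or standardisation. The same section mentions a reference for levels, "We will assess whether AM blood serum levels lie within therapeutic range at t1", but only as a separate check that is not carried into the correlation.

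Section 4.2 lists the eligible drugs: "citalopram: 20-40mg, escitalopram: 10-20mg, sertraline: 75-150mg, venlafaxine: 75-150mg, duloxetine: 60-100mg, paroxetine: 20-40mg", and as a seventh, from another class, "NaSSA (mirtazapine: 30-45mg".

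Section 2.2 stratifies randomisation by "risk of developing discontinuation symptoms associated with the antidepressant medication (moderate vs. higher or unknown risk, 1:1". Section 5.3.1 puts this factor into the primary ANCOVA ("The following stratification variables of the randomization process"), and the section 5.3.2 models carry it as well.

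**The concern.** A correlation between two variables is confounded by anything related to both. Drug is a candidate on both sides.

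- **Drug and symptom load.** This link is the trial's own premise. The SAP treats drug-associated risk as prognostic by stratifying on it and adjusting for it.
- **Drug and serum level.** This link is an inference. The eligible drugs differ in class and in dose range, so it is reasonable to expect different concentration scales, but the SAP prints no serum values.

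Randomisation does not remove the problem. Serum level is not randomised, and both discontinuation groups contain a mixture of drugs.

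A directional hypothesis is attached, so a positive pooled coefficient would be reported as support for it and a null or negative one as evidence against it. Either could come from which drugs the patients take, whatever the relation among patients on the same drug.

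**Working it through.** **Number of patients.** The SAP gives no figure for the correlation itself. Section 2.3 gives 42 evaluable and 49 recruited patients per group. The two discontinuation groups therefore hold 2 × 42 = 84 evaluable to 2 × 49 = 98 recruited patients. The total behind this reproduces: f = 0.22, two-sided alpha 0.05, power 80% and one numerator degree of freedom give N = 165, or 168 in four equal groups (power 0.809).

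**Spurious correlation with two equal strata.** Let dx be the gap in mean log level and dy the gap in mean symptom load between the risk strata, each in within-drug SDs. Section 2.2 gives the strata as 1:1. With no within-drug relation,

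r = 0.25·dx·dy / √[(1 + 0.25·dx²)(1 + 0.25·dy²)].

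The values of dx and dy are assumptions; no document gives them.

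- dx = 1.5, dy = 0.3: r = 0.1125 / √(1.5625 × 1.0225) = 0.09. An observed r of this size has p = 0.42 at n = 84 and p = 0.38 at n = 98.
- dx = 3, dy = 0.8: r = 0.60 / √(3.25 × 1.16) = 0.31. Here p = 0.004 at n = 84 and p = 0.002 at n = 98.

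The sign reverses if the higher-risk drugs have the lower levels.

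**Chance of a false positive.** By Fisher's z, P(p < 0.05) = 1 − Φ(1.96 − z) + Φ(−1.96 − z), with z = atanh(r)·√(n − 3). At n = 84, r = 0.089 gives z = 0.80 and a probability of 13%; r = 0.309 gives z = 2.88 and 82%. The nominal rate is 5%.

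**Allowing for spread within a stratum.** The formula gives every drug in a stratum the same mean level. If drug means also vary within a stratum with SD τ (in within-drug SDs), the level term becomes 1 + τ² + 0.25·dx². With τ = 1 as an example, the two results fall to 0.1125 / √(2.5625 × 1.0225) = 0.07 and 0.60 / √(4.25 × 1.16) = 0.27.

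**A check on the plan's own drug list.** Midpoints of the dose ranges run from 15 mg to 112.5 mg, a ratio of 7.5. Take log mid-dose as a stand-in for concentration scale, a within-drug log SD of 0.5, equal use of the seven drugs and dy = 0.5 (all assumptions). Over every division of the seven drugs into risk groups of three and four:

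- the spurious r ranges from −0.18 to +0.18, with mean absolute value 0.07;
- at the extremes, about 38% of simulated tests at n = 84 reach p < 0.05 with no within-drug relation;
- centring level and load within drug brings this back to about 5%, with mean r of 0.00.

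**Attenuation without any risk difference.** On the same stand-in, the variance of the drug means is 2.04 in within-drug units. A true within-drug r of 0.30 becomes 0.30 / √(1 + 2.04) = 0.17. Simulated power at n = 84 is 34% pooled and 77% drug-centred.

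**Both together.** With a true within-drug r of 0.30 and dy = 0.8, the mean pooled r is −0.12 or 0.44 at the two extreme divisions. The drug-centred value stays at 0.30.

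**The case against.** The strongest reply has four parts.

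1. **The method is loosely described rather than fixed.** Section 5.6 speaks of correlation analyses in the plural and does not say that levels are raw or that all drugs are pooled. A partial or per-drug correlation is not ruled out. This stands as a limit on the wording, but no such analysis is planned, and the plan as written contains nothing that would separate drugs.
2. **Only one of the two links is documented.** Section 4.2 gives oral doses, not serum levels. This stands: the conclusion is conditional on concentration scales differing.
3. **The size may be small.** At the lower end of the illustration r is 0.09, and some divisions of the drugs by risk give almost no bias. The second stratum also includes drugs of unknown risk, which may dilute the contrast in load. This stands too, and the SAP does not say which drug belongs to which stratum.
4. **Little depends on it.** The analysis is exploratory, is not an endpoint, and leaves the primary model untouched. That is right, and it sets the weight of the point.

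A reader might go further and infer that the correlation mainly compares drugs, or that it cannot test the hypothesis at all. The document does not support either. The between-drug share depends on concentrations and a drug-to-risk assignment that are not given. Nor does the SAP say that its hypothesis concerns patients on the same drug; that is the natural reading, but it is an interpretation.

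**Conclusion.** The point holds as a minor one. Followed as written, the section 5.6 correlation mixes between-drug and within-drug differences, and its result could not be attributed to either.

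The conclusion rests on one premise from the SAP, that drug-associated risk is prognostic for symptom load, and one assumption, that concentration scales differ between drugs. Under the illustrative gaps the spurious correlation is about 0.09 to 0.31 in absolute value, from negligible to clearly significant, and lower once levels vary within a stratum. Neither its actual size nor its sign can be determined from the document. Attenuation is possible even if drugs carry the same risk. No primary, secondary or safety conclusion is affected.

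**What to change.** Replace the unspecified correlation in section 5.6 with a linear regression, in the two discontinuation groups, of DESS AUC on log serum level at t1 with drug as a factor, adding t1 DESS and expectation group as covariates. Report the common within-drug slope with its 95% CI as the exploratory result. The drug factor removes the between-drug component. If the risk stratum is determined by drug alone, the factor absorbs that as well.

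The cost is one or two sentences in the SAP and no new data. Seven drugs use 7 − 1 = 6 degrees of freedom out of 84 to 98 patients. A drug taken by a single patient contributes nothing to the slope, so the number of patients per drug should be reported alongside it.
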